		14.5.1.4.1 EQ-5D-5L: Individual Categories – Full Analysis Set
		14.5.1.4.2 EQ-5D-5L: Individual Categories – Per Protocol Set
		14.5.1.5.1 EQ-5D-5L VAS and Index Score: Actual Values and Changes from Baseline – Full Analysis Set
		14.5.1.5.2 EQ-5D-5L VAS and Index Score: Actual Values and Changes from Baseline – Per Protocol Set
		14.5.1.6.1 EQ-5D-5L Repeated-Measures Model for Analysis of Treatment Difference (Index Score)– Full Analysis Set
		14.5.1.6.2 EQ-5D-5L Repeated-Measures Model for Analysis of Treatment Difference (Index Score) – Per Protocol Set

Type*	Section	Title
L	16.2 Individual Subject Data Listing	16.2.1.1 Subject Disposition and Study Termination Information – All Screened Population
		16.2.1.2 Randomisation Scheme and Codes (Subject Identification) – All Randomised Set
		16.2.1.3 Start of Treatment after Randomisation Date – All Randomised Set
		16.2.2.1.1 Description of Inclusion and Exclusion Criteria
		16.2.2.1.2 Inclusion and Exclusion Criteria – Screen Failure Subjects
		16.2.2.2 Admission and Discharge Dates – All Randomised Set
		16.2.2.3.1 Description of Protocol Violation Categories
		16.2.2.3.2 Protocol Violations – All Randomised Set
		16.2.3.1 Subject Populations – All Screened Set
		16.2.3.2 Subjects Excluded from Efficacy Analyses – All Randomised Set
		16.2.4.1.1 Demographics – All Randomised Set
		16.2.4.1.2 Demographics – Screen Failure Subjects
		16.2.4.2 Index Hospitalisation Information – All Randomised Set
		16.2.4.3 History of Cardiovascular Risk Factors – All Randomised Set
		16.2.4.4 Symptoms and Signs of Heart Failure at Time of Index Hospitalisation – All Randomised Set
		16.2.4.5 Other Baseline Disease Characteristics – All Randomised Set
		16.2.4.6 Acute Heart Failure Hospitalisation History – All Randomised Set
		16.2.4.7 Medical History – All Randomised Set
		16.2.4.8 Acute Heart Failure Local Laboratory Blood Test – All Randomised Set
		16.2.5.1 Dosing Information – Safety Analysis Set
		16.2.5.2 Compliance Information – Safety Analysis Set
		16.2.6.1 Efficacy Response Data up to 52 Weeks after Randomisation – Full Analysis Set
		16.2.6.2 Efficacy Response Data up to 30 Days after Randomisation – Full Analysis Set
		16.2.6.3 Efficacy Response Data up to the Last available value – Full Analysis Set
		16.2.6.4.1 Events Adjudicated by Clinical Endpoint Committee – Full Analysis Set
		16.2.6.4.2 Events Adjudicated by Individual Adjudicators – Full Analysis Set
		16.2.6.5 Hospitalisation Details – Full Analysis Set
		16.2.6.6 NYHA Functional Class – Full Analysis Set
		16.2.7.1 All Adverse Events – Safety Analysis Set
		16.2.7.2 Serious Adverse Events – Safety Analysis Set
		16.2.7.3 Adverse Events Leading to Study Product Discontinuation – Safety Analysis Set
		16.2.7.4 Death Details – Safety Analysis Set
		16.2.7.5 Hypersensitivity Reactions – Safety Analysis Set
		16.2.7.6 Non-Treatment Emergent Adverse Events – Safety Analysis Set
		16.2.7.7 Adverse Events between Randomisation and Start of Treatment – Safety Analysis Set
		16.2.8.1 Local Laboratory Results – Safety Analysis Set

Type*	Section	Title
		16.2.8.2 Serum Pregnancy Test – Safety Analysis Set
		16.2.9.1 Vital Signs – Safety Analysis Set
		16.2.9.2 Electrocardiograms – Safety Analysis Set
		16.2.9.3 Special Situations – Full Analysis Set
		16.2.9.4 Symptoms and Signs of Heart Failure – Full Analysis Set
		16.2.9.5 Concomitant and Prior Medications – Full Analysis Set
		16.2.9.6 Concomitant and Prior Procedures – Full Analysis Set
		16.2.9.7 Pregnancy – Details of Mother and Current Pregnancy – Full Analysis Set
		16.2.9.8 Pregnancy – Drug Exposure during Pregnancy – Full Analysis Set
		16.2.9.9 Pregnancy – Outcome of Pregnancy, Baby Information – Full Analysis Set
		16.2.10.1 KCCQ-12 – Full Analysis Set
		16.2.10.2 EQ-5D-5L – Full Analysis Set
F	14.1 Disposition/Demographics/Other Characteristics	14.1.1.1 KM Curves for Time to Discontinuation – Full Analysis Set
F	14.2 Efficacy	14.2.1.1 Cumulative Risk over Time for HF Hospitalisations or CV Deaths– Full Analysis Set
		14.2.1.2 Cumulative Risk over Time for HF Hospitalisations or CV Deaths– Per Protocol Set
		14.2.2.1.1 Cumulative Risk over Time for CV Hospitalisations or CV Deaths– Full Analysis Set
		14.2.2.1.2 Cumulative Risk over Time for CV Hospitalisations or CV Deaths– Per Protocol Set
		14.2.2.2.1 Cumulative Risk over Time for HF Hospitalisations – Full Analysis Set
		14.2.2.2.2 Cumulative Risk over Time for HF Hospitalisations – Per Protocol Set
		14.2.2.3.1 Cumulative Risk over Time for CV Hospitalisations – Full Analysis Set
		14.2.2.3.2 Cumulative Risk over Time for CV Hospitalisations – Per Protocol Set
F	14.2.3 Subgroup Analyses	14.2.3.1 Forest Plot of Rate Ratios for HF Hospitalisations and CV Deaths up to 52 Weeks after Randomisation – Full Analysis Set
		14.2.3.2 Forest Plot of Rate Ratios for CV Hospitalisations and CV Deaths up to 52 Weeks after Randomisation – Full Analysis Set
		14.2.3.3 Forest Plot of Rate Ratios for HF Hospitalisations up to 52 Weeks after Randomisation – Full Analysis Set
		14.2.3.4 Forest Plot of Hazard Ratios for CV Death up to 52 Weeks after Randomisation – Full Analysis Set
		14.2.3.5 Forest Plot of Hazard Ratios for Composite of HF Hospitalisations or CV Death up to 52 Weeks after Randomisation – Full Analysis Set
		14.2.3.6 Forest Plot of Rate Ratios for Days Lost due to HF Hospitalisations or CV Death up to 52 Weeks after Randomisation – Full Analysis Set

Type*	Section	Title
		14.2.3.7 Forest Plot of Odds Ratios for NYHA Functional Class – Full Analysis Set

*T = Table, L = Listing, F = Figure.

8. APPENDICES

Appendix I: Protocol Deviations

	Standard name of the deviation	Deviation code	Major/Potentially Critical	Statistical Assessment of the deviations
	Inclusion Criteria			
1	
Hospitalised for ADHF, one of the following items a to d not confirmed:
 
a) Upon admission for the AHF episode, persistent dyspnoea at rest in a recumbent sitting position (30-45o) or with minimal exertion
 
b) Upon or during the AHF admission, at least two of the following clinical findings were present:
 
i. Congestion on chest x-ray
 
ii. Rales on chest auscultation
 
iii. Oedema > 1+ on a 0-3+ scale
 
iv. Elevated jugular venous pressure (> 8cm H2O)
 
c. Natriuretic peptide levels, measured ≤72 hours (for protocol version 3.0) or ≤24 hours (for protocol version 1.1, 2.0) of the AHF admission must have been:
 
i. Brain natriuretic peptide (BNP) ≥400 pg/mL or N-terminal-pro-brain natriuretic peptide (NT-proBNP) ≥1,600 pg/mL or
 
ii. BNP ≥600 pg/mL or NT-proBNP ≥2,400 pg/mL for subjects presenting with atrial fibrillation when the blood sample was taken
 
iii. For subjects treated with an angiotensin receptor neprilysin inhibitor (ARNI) in the previous 4 weeks prior to randomisation only NT proBNP values should be considered (for protocol version 2.0, 3.0)
 
d. AHF episode treated with minimally 40 mg of IV furosemide (or equivalent IV loop diuretic defined as 20 mg of torsemide or 1 mg of bumetanide)
	PDINC01	Major	Excluded from PP
2	Subject is not or not confirmed iron deficient defined as serum ferritin <100 ng/mL or 100 ng/mL ≤ serum ferritin ≤299 ng/mL if TSAT <20%.	PDINC02	Major	Excluded from PP

	Standard name of the deviation	Deviation code	Major/Potentially Critical	Statistical Assessment of the deviations
3	Subject not having a Left ventricular ejection fraction <50% (assessed and documented within 12 months prior to randomisation).	PDINC03	Major	Excluded from PP
4	Subject not male or female aged ≥18 years old	PDINC04	Major	Excluded from PP
5	Subject (or legally acceptable representative) has not provided the appropriate written informed consent. Subject must provide written informed consent before any study-specific procedures are performed	PDINC05	Major	Excluded from the analyses (FAS and PP)
Exclusion Criteria				
1	Subject with dyspnoea due to non-cardiac causes such as acute or chronic respiratory disorders or infections (i.e., severe chronic obstructive pulmonary disease, acute bronchitis, pneumonia, primary pulmonary hypertension).	PDEXC01	Major	Individual cases with potential impact on the primary endpoint might be excluded from PP (case review prior unblinding required)
2	Subject with temperature >38°C (oral or equivalent), active infective endocarditis, sepsis, systemic inflammatory response syndrome, or any other active infection requiring anti-microbial treatment at any time during an Index hospitalisation.	PDEXC02	Major	Individual cases with potential impact on the primary endpoint might be excluded from PP (case review prior unblinding required)
3	Subject with documented restricted amyloid cardiomyopathy, or acute myocarditis or hypertrophic obstructive, restrictive, or constrictive cardiomyopathy.	PDEXC03	Major	Individual cases with potential impact on the primary endpoint might be excluded from PP (case review prior unblinding required)
4	Subject with clinical evidence of acute coronary syndrome, transient ischemic attack or stroke, within the last 30 days prior randomisation	PDEXC04	Major	Individual cases with potential impact on the primary endpoint might be excluded from PP (case review prior unblinding required)
5	Subject with severe valvular or left ventricular outflow obstruction disease needing intervention.	PDEXC05	Major	Individual cases with potential impact on the primary endpoint might be excluded from PP (case review prior unblinding required)
6	Subject with coronary-artery bypass graft, cardiac resynchronisation therapy device implantation, percutaneous intervention (e.g., cardiac, cerebrovascular, aortic) or major surgery that led to significant blood loss, including thoracic and cardiac surgery, within the last 3 months prior to randomisation.	PDEXC06	Major	Individual cases with potential impact on the primary endpoint might be excluded from PP (case review prior unblinding required)

	Standard name of the deviation	Deviation code	Major/Potentially Critical	Statistical Assessment of the deviations
7	Subject has a body weight <35 kg at randomisation	PDEXC07	Major	Individual cases with potential impact on the primary endpoint might be excluded from PP (case review prior unblinding required)
8	Subject randomized despite an immediate need of transfusion or with a Hb <8 g/dL or with a Hb >15 g/dL	PDEXC08	Major	Individual cases with potential impact on the primary endpoint might be excluded from PP (case review prior unblinding required)
9	Subjects on treatment for Vitamin B ₁₂ and/or serum folate deficiency. Note: Use of Vitamin B ₁₂ and folic acid as supplement therapy (not for deficiency treatment) is permitted.	PDEXC09	Major	Individual cases with potential impact on the primary endpoint might be excluded from PP (case review prior unblinding required)
10	Subject with a known anaemia not attributed to ID (e.g., other microcytic anaemia) or with an evidence of iron overload (e.g., haemochromatosis) or disturbances in the utilisation of iron.	PDEXC10	Major	Individual cases with potential impact on the primary endpoint might be excluded from PP (case review prior unblinding required)
11	Subject with a known hypersensitivity to any of the study products to be administered or known serious hypersensitivity to other parenteral iron products	PDEXC11	Major	Individual cases with potential impact on the primary endpoint might be excluded from PP (case review prior unblinding required)
12	Subject with known severe allergies including drug allergies, history of severe asthma, eczema or other atopic allergy and in subjects with immune or inflammatory conditions (e.g., systemic lupus erythematosus, rheumatoid arthritis).	PDEXC12	Major	Individual cases with potential impact on the primary endpoint might be excluded from PP (case review prior unblinding required)
13	Subject with a history of erythropoietin stimulating agent, IV iron therapy, and/or blood transfusion in previous 3 months prior to randomisation.	PDEXC13	Major	Individual cases with potential impact on the primary endpoint might be excluded from PP (case review prior unblinding required)
14	Subject on treatment with oral iron therapy at doses >100 mg/day in previous 4 weeks prior to randomisation.	PDEXC14	Major	Individual cases with potential impact on the primary endpoint might be excluded from PP (case review prior unblinding required)
15	Subjects currently receiving systemic chemotherapy and/or radiotherapy.	PDEXC15	Major	Individual cases with potential impact on the primary endpoint might be excluded from PP (case review prior unblinding required)

	Standard name of the deviation	Deviation code	Major/Potentially Critical	Statistical Assessment of the deviations
16	Subjects on renal dialysis (previous, current or planned within the next 6 months).	PDEXC16	Major	Individual cases with potential impact on the primary endpoint might be excluded from PP (case review prior unblinding required)
17	Subject has known history of malignancy of any organ system (except non-invasive basal cell carcinoma, squamous cell carcinoma of the skin or cervical intra-epithelial neoplasia) within the last 5 years	PDEXC17	Major	Individual cases with potential impact on the primary endpoint might be excluded from PP (case review prior unblinding required)
18	Subject has a terminal illness other than HF with expected survival <12 months.	PDEXC18	Major	Individual cases with potential impact on the primary endpoint might be excluded from PP (case review prior unblinding required)
19	Subjects with a chronic liver disease (including active hepatitis) and/or alanine transaminase or aspartate transaminase above 3 times the upper limit of the normal range.	PDEXC19	Major	Individual cases with potential impact on the primary endpoint might be excluded from PP (case review prior unblinding required)
20	Subjects with known hepatitis B surface antigen positivity and/or hepatitis C virus ribonucleic acid positivity.	PDEXC20	Major	Individual cases with potential impact on the primary endpoint might be excluded from PP (case review prior unblinding required)
21	Subject previously randomised into this study.	PDEXC21	Major	Major: Other action - Subject will only be handled in the ITT population with the first enrolment into the study
22	Subject is currently enrolled in or has completed any other investigational device or drug study <30 days prior to screening, or is receiving other investigational agent(s).	PDEXC22	Major/minor case by case review required	Individual cases with potential impact on the primary endpoint might be excluded from PP (case review prior unblinding required)
23	Subject is pregnant (e.g., positive human chorionic gonadotropin test) or breast feeding.	PDEXC23	Major	Individual cases with potential impact on the primary endpoint might be excluded from PP (case review prior unblinding required)
24	If of childbearing potential, subject is not using adequate contraceptive precautions. Subject must agree to use adequate contraception during the study and for 1 month after the last dose of study treatment. A highly effective method of birth control must be used.	PDEXC24	Major/minor case by case review required	Individual cases with potential impact on the primary endpoint might be excluded from PP (case review prior unblinding required)

	Standard name of the deviation	Deviation code	Major/Potentially Critical	Statistical Assessment of the deviations
25	Subject has a history of drug or alcohol abuse within 2 years prior to screening.	PDEXC25	Major	Individual cases with potential impact on the primary endpoint might be excluded from PP (case review prior unblinding required)
26	Subject has a significant medical condition(s), anticipated need for major surgery during the study, or any other kind of disorder that may be associated with increased risk to the subject, or may interfere with study assessments, outcomes, or the ability to provide written informed consent or comply with study procedures, in the Investigator's opinion.	PDEXC26	Major	Individual cases with potential impact on the primary endpoint might be excluded from PP (case review prior unblinding required)
Study procedures				
1	In case of ICF updates during the course of the study: Subject (or legally acceptable representative) has not provided the appropriate written informed consent in case of an informed consent update.	PDSPR01	Major	Individual cases with potential impact on the primary endpoint might be excluded from PP (case review prior unblinding required)
2	Subject (or legally acceptable representative) has not provided the appropriate written informed consent for the Biomarker sub-study but samples were collected.	PDSPR01b	Major	None
3	Subjects with missing local laboratory assessment specific to the study (or with local lab values not evaluable due to logistical reasons, eg wrong handling of samples) or missing physical examination.	PDSPR02	Minor	None
4	Subjects with local Lab results missing at post randomization visits to determine if ID persists and to obtain Hb values	PDSPR03	Major	None
5	Subjects with not completed KCCQ, EQ-5D questionnaires and/or not available NYHA classification.	PDSPR04	Minor	None
6	Subjects with missing ECG assessment at baseline and Visit 6 or with a missing ECG scan uploaded in the eCRF.	PDSPR05	Minor	None
7	Subjects with study visit OOW as defined in the protocol	PDSPR06	Minor	None
8	Subjects with missed study visit (phone or on-site)	PDSPR07	Major	None

	Standard name of the deviation	Deviation code	Major/Potentially Critical	Statistical Assessment of the deviations
9	Subjects that consented for the biomarker substudy but with biomarker sample collection missing (or with local lab values not evaluable due to logistical reasons, eg wrong handling of samples); Or other deviations to biomarker sampling	PDSPR08	Minor	None
10	Subject anonymity is not maintained in source documents uploaded ECGs, for SAE/safety and / or adjudication purposes.	PDSPR09	Major	None
11	Subjects with study visits performed as telephone calls instead of physical visits	PDSPR10	Minor	None
12	Subjects with assessments done in extent to the protocol defined assessments at respective visits (eg additional EQ5D questionnaires at additional visits)	PDSPR11	Minor	None
13	Subjects with assessments done at visits in the wrong order (eg lab assessments prior the questionnaires, questionnaires at the day of the visits/calls or collecting the laboratory values from different blood drawings) or by the wrong study staff	PDSPR12	Minor	None
14	Subjects received treatment prior stabilisation from IV diuretics	PDSPR13	Minor	None
15	Site blinding plan not followed (study staff performing assessments not assigned to)	PDSPR14	Major	None
16	Post-randomisation study drug given based on Labs done more than 7 days	PDSPR15	Minor	None
17	Inconsistencies in the ICF consent procedure e.g. date differences...	PDSPR16	Major	None
Investigational Medicinal Product				
1	Subjects who received Incorrect IMP dosing based on subject BW at baseline & Hb value at screening	PDIMP01	Major	Excluded from PP
2	Subjects with ID who was administered Incorrect IMP dosing based on subject BW & Hb value at post-baseline dosing visits (Weeks 6, 12, 24) or subject without ID who was administered IMP dosing post-baseline - lower dosage than assigned	PDIMP02a	Major	Excluded from PP

	Standard name of the deviation	Deviation code	Major/Potentially Critical	Statistical Assessment of the deviations
	Subjects with ID who was administered Incorrect IMP dosing based on subject BW & Hb value at post-baseline dosing visits (Weeks 6, 12, 24) or subject without ID who was administered IMP dosing post-baseline -- higher dosage than assigned	PDIMP02b	Major	Excluded from PP
3	Subject who missed one or more doses of IMP	PDIMP03	Major	Excluded from PP
4	Subject received incorrect treatment allocation	PDIMP04	Major	None
5	Subject received treatment but failed to attend any post-baseline visit or assessment	PDIMP05	Major	Excluded from the analyses (FAS and PP)
6	Subject received study treatment not according to the administration guidelines (including undiluted bolus IV injection, duration of injection, using blinding measures as a black syringe or a curtain)	PDIMP06	Major	None
7	Subjects with IMP administered by someone other than assigned unblinded study staff	PDIMP07	Major	None
8	Subjects with events that led to unblinding of the study treatment without an emergency situation	PDIMP08	Major	Individual cases with potential impact on the primary endpoint might be excluded from PP (case review prior unblinding required)
9	Subjects with dosing of IMP not at the time point of randomization prior discharge, or randomization not done at last day of hospital discharge	PDIMP09	Major	Individual cases with potential impact on the primary endpoint might be excluded from PP (case review prior unblinding required)
10	Deviations on IMP handling like, shipment destruction prior IMP reconciliation is made or IMP storage	PDIMP10	Minor	None
11	Subjects with administration of expired IMP or IMP with deviations in the temperature log	PDIMP11	Major	Excluded from PP
12	Subject took study treatment after intake of forbidden Concomitant medication	PDIMP12	Major	Individual cases with potential impact on the primary endpoint might be excluded from PP (case review prior unblinding required)
	Other			

	Standard name of the deviation	Deviation code	Major/Potentially Critical	Statistical Assessment of the deviations
1	Unreported SAE detected by oversight activities like source data verification (not reported within 24 hours)	PDOTH01	Major	None
2	Unreported Special Situations detected by oversight activities like source data verification	PDOTH02	Minor	None
3	Entries in EDC or Source data either not available or incomplete for SDV in a timely manner	PDOTH03	Minor	None
Withdrawal from study treatment/follow ups				
1	Subject withdrew from follow up but information was collected after withdrawal consent	PDWITH01	Major	Individual cases with potential impact on the primary endpoint might be excluded from PP (case review prior unblinding required)
2	Subject withdrew from study treatment but continued receiving study treatment	PDWITH02	Major	Individual cases with potential impact on the primary endpoint might be excluded from PP (case review prior unblinding required)
Observations detected but not classified as PD				
1	Subject with intake of forbidden Concomitant medication but patient withdrawal from study medication	TRACK01	NA	NA
2	Subject with incorrect entries for the randomisation factors at baseline	TRACK02	NA	NA
3	Subject randomized by mistake and never received the IMP	TRACK03	NA	NA

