12.3.2 Per-protocol Set

The per-protocol (PP) analysis set will consist of all subjects who, in addition to the FAS criteria, had no major protocol violations (as defined in the SAP).

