16. PROCEDURE FOR MODIFICATION OF PROTOCOL OR PREMATURE TERMINATION OF THE STUDY

16.1 Protocol Waivers, Deviations and Violations

Protocol waivers shall not be permitted except where necessary to eliminate an immediate hazard to subjects.

Deviations from the protocol including violations of inclusion/exclusion criteria will be assessed as minor or major on a case-by-case basis. The criteria describing the deviation(s) and how they will be handled will be documented in the SAP.

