3. ANALYSIS POPULATIONS

3.1. Population Definitions

The following subject populations will be evaluated and used for presentation and analysis of the data:

Screened population

The screened population will consist of all subjects who signed an informed consent form.

All Randomised

The All Randomised set will consist of all subjects randomised to either of the two treatment groups. The All Randomised set will be analysed based on the randomised treatment arm.

Full Analysis Set

The Full Analysis Set (FAS) will consist of all subjects who satisfy the following criteria:

- Randomised to either of the two treatment groups, and
- The administration of study drug was started.
- At least one post-baseline visit (including calls), death or hospitalisation or subjects without post-baseline assessment who withdrew from the study after but not on the randomisation date.

Additionally, subjects with protocol deviation concerning inclusion criteria no. 5 (*Subject (or legally acceptable representative) has provided the appropriate written informed consent. Subject must provide written informed consent before any study-specific procedures are performed.*) will be excluded from FAS.

Subjects in the FAS will be analysed based on their randomised treatment arm.

Per-Protocol Set

The Per-Protocol (PP) analysis set will consist of all subjects in the FAS who had no major protocol violations (see Appendix I).

Safety Set

The Safety (SAF) analysis set will consist of all randomised subjects for whom the administration of study drug has started. Subjects will be analysed according to the treatment received.

The analysis sets to be used for analyses are described in the table below.

Table 2 Analysis Sets

Analyses	Screened population	All Randomised	FAS	PP	SAF
Subject disposition	✓	✓			
Protocol deviations/violations		✓			
Demographics			✓	✓	✓
Baseline characteristics (prior, concomitant and newly started medications, medical history including surgical history and procedures)			✓	✓	✓
Prior medications, concomitant, newly started medications			✓		✓
Medical History and history of cardiovascular factors.			✓	✓	✓
Compliance and exposure					✓
Primary endpoint			✓	✓	
Secondary endpoints			✓	✓	
Other endpoints			✓	✓	
KCCQ-12			✓	✓	
EQ-5D			✓	✓	
AEs, SAEs, and special situations					✓
Event Adjudications					✓
Laboratory parameters					✓
ECGs					✓
Vital Signs					✓

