3.2. Protocol Deviations/Violations

The sponsor, or designee, will be responsible for producing the final protocol deviation/violation file (formatted as an Excel file or SAS dataset), in collaboration with Cytel and the data monitoring group as applicable; this file will include a description of each protocol deviation/violation, and will clearly identify whether or not each violation warrants exclusion from a population. This file will be finalized prior to hard database lock.

Protocol deviations will be reported in a data listing for all subjects in the All randomised.

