4.4. Subject Disposition

Subject disposition will be tabulated based on the screened population and will include the number screened subjects, randomised subjects, screened failures and subjects re-screened and randomised. If subject is re-screened, such subject will be calculated only once in the screened population. The reason for screen failure will be provided. All screen failure reasons including reasons if subject was re-screened, will be summarized.

In addition, the number of subjects randomised, treated, started treatment after and not on the randomisation date, randomised not-treated, who received a different treatment that they were randomised to, who discontinued treatment, discontinued study, discontinued treatment but completed study along with the reason for treatment discontinuation and the reason for study discontinuation will be provided based on All Randomised Set. The number of subjects in each population with reason for exclusion will be provided based on All Randomised population.

A by-subject listing of study withdrawal/completion information, including the reason for premature study withdrawal, if applicable, will be presented.

Protocol deviations will be listed.

In addition, Kaplan-Meier (KM) curves for time to discontinuation, censoring at last visit (see section 4.2.13), will be plotted by treatment group for the FAS.

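### SAP 3.1 and Appendix I disagree on whether a subject given the wrong treatment belongs in the per-protocol set (PDIMP04: Major, but action None)

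*SAP*

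**What the plan says.** SAP 3.1 defines the PP set as "all subjects in the FAS who had no major protocol violations (see Appendix I". Protocol 12.3.2 has the same rule, adding to the FAS criteria that subjects "had no major protocol violations (as defined in the SAP", so the meaning of major is left to the SAP. Protocol 16.1 gives the SAP the handling as well: "The criteria describing the deviation(s) and how they will be handled will be documented in the SAP".

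In Appendix I, under Investigational Medicinal Product, PDIMP04 reads "Subject received incorrect treatment allocation". It is classed Major and its statistical assessment is None.

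SAP 3.2 adds a final deviation file, completed before hard database lock, that "will clearly identify whether or not each violation warrants exclusion from a population". SAP 4.4 foresees wrong-treatment cases: the disposition table counts subjects "who received a different treatment that they were randomised to".

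On the arm used for analysis, SAP 3.1 says: "Subjects in the FAS will be analysed based on their randomised treatment arm". The safety set is analysed by treatment received. No arm rule is given for PP.

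**The concern.** Two written rules give two different PP sets. Under the definition a Major violation is disqualifying; under the action column this one has no consequence.

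The action is also out of line with the rows around it. A subject given the assigned product at the wrong volume is excluded; a subject given the unassigned product is not, and is not even sent for case review. Neither document explains this ordering.

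At stake is the meaning of the PP analysis, which is the sensitivity analysis for the primary, secondary and other endpoints. It is meant to show the result among subjects treated as planned. If subjects who received the other arm's product remain in their randomised arm and the treatment works, each arm is diluted with the other and the PP estimate moves toward no effect.

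**Working it through.** **Text comparison.** The relevant rows of Appendix I, all classed Major:

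| Code | Deviation (paraphrased) | Action |
|---|---|---|
| PDIMP01 | Wrong first dose for weight and Hb | Excluded from PP |
| PDIMP02a/b | Lower or higher post-baseline dose than assigned | Excluded from PP |
| PDIMP03 | One or more doses missed | Excluded from PP |
| PDIMP11 | Expired product or temperature-log deviation | Excluded from PP |
| PDIMP08 | Unblinding without an emergency | Case review before unblinding |
| PDIMP09 | Dosing or randomisation at the wrong time | Case review before unblinding |
| PDIMP04 | Incorrect treatment allocation | None |

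Applying 3.1 literally, PDIMP04 is Major, so the subject is out. Applying the action column, the subject is in. Nine other codes share the Major/None pattern: PDSPR01b, 03, 07, 09, 14 and 16; PDIMP06 and 07; PDOTH01. Most exclusion-criterion codes are Major with only a possible exclusion after review. This suggests that the action column, not the Major label, was meant to decide membership, but 3.1 does not say so.

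**Size.** The documents contain no figure for this point, so what follows is an illustration on the design assumptions.

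The design rate ratio reproduces from Protocol 12.2 and SAP 4.1. Placebo: 12 + 2 × (35 − 6) = 70 events per 100 years. FCM, with 30% fewer HF hospitalisations and unchanged CV death: 12 + 0.7 × 58 = 52.6. Ratio: 52.6/70 = 0.751, stated as 0.75.

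Now let a share x of each arm receive the other treatment for the whole follow-up and be analysed as randomised:

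observed ratio = [0.75(1 − x) + x] / [(1 − x) + 0.75x]

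- x = 1%: 0.7525/0.9975 = 0.754 (5.5 of 550 per arm)
- x = 2%: 0.7550/0.9950 = 0.759 (11 per arm)
- x = 3%: 0.7575/0.9925 = 0.763 (16.5 per arm)

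Crossover in one direction only does less. At 1%, it gives 0.75/0.9975 = 0.752 if only placebo subjects receive FCM, and 0.7525 if only FCM subjects receive placebo. One wrong kit among several doses would also normally do less than a full-course swap. Strictly, x is a share of the PP set, so with other exclusions the same number of subjects is a slightly larger share.

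**The case against.** A reader might infer that wrong-treatment subjects definitely stay in PP and that cross-arm contamination is built into it. The documents do not support that, for three reasons.

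- Retention is one of two readings. The wording of 3.1 alone would exclude these subjects, and the deviation file in 3.2 could still flag them. This stands. However, a flag that departed from Appendix I would be a late decision in place of a written rule.
- The code need not mean a crossover. The protocol uses allocation for numbered treatment packs as well (6.1, 7.4, 9.2.3.12), so PDIMP04 may include a wrong pack from the correct arm. None is sensible for that case. This stands, and the fix separates the two.
- The arm used for PP is inferred from PP being a subset of the FAS. If PP were analysed by treatment received, this dilution would not arise, but the comparison would no longer be by randomised arm.

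The other side can also say that little turns on it. PP is only a sensitivity analysis, dilution toward no effect is conservative in a superiority trial, and doses after the first are conditional, so there may be few chances of a mix-up. All of this limits the importance; none of it removes the contradiction.

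Finally, correcting PDIMP04 alone would leave 3.1 and Appendix I in conflict for nine other codes, and telling an other-arm kit from a same-arm kit needs allocation data. Both points are right and shape the fix.

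**Conclusion.** The point holds as a contradiction between SAP 3.1 and the Appendix I action for PDIMP04. The likelier outcome under the more specific rule is hard to justify beside the neighbouring rows. That these subjects remain in PP, and in their randomised arm, is the more natural reading but not a stated fact.

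The consequence is small. At 1% to 2% full-course, symmetric crossover, 0.75 becomes about 0.754 to 0.759, and partial or one-way mix-ups would normally do less. The documents give no expected rate. The FAS primary analysis rightly keeps such subjects as randomised, and the safety set counts them by treatment received; neither is affected. This is a minor correction that makes the PP set unambiguous.

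**What to change.** Before unblinding:

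1. In Appendix I, set PDIMP04 to Excluded from PP when any administered kit came from the arm not assigned. Keep None for a wrong kit number of the correct arm.
2. Write this as a deterministic rule and apply it by program from the kit and randomisation lists, so that no blinded reviewer needs allocation data. Add a sentence to 3.2 saying that this one exclusion is derived in that way and not by case review.
3. In 3.1, state that PP membership follows the Appendix I action column. This settles PDSPR01b, 03, 07, 09, 14 and 16, PDIMP06 and 07, and PDOTH01 without changing their rows.
4. In 3.1, state that PP is analysed by randomised arm.

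The cost is one table row split in two, a few sentences and a short derivation. Subjects who received a different treatment are already to be counted for the disposition table in 4.4. The downside is a handful fewer subjects in PP. FAS and safety set rules stay as they are.
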